**Table 2. Study visits and procedures**

Visit	Procedure
Day 1	Pre-treatment scan, blood draw, and medication randomization. After the scan, subjects will receive a blister-pack containing study medication and will take the first dose at the study site in front of study personnel.
Day 7	Post-treatment scan and blood draw. Before the scan, drinking over the previous six days will be assessed. LFTs will be repeated on this day or the following day, after medication administration is complete.
Day 8	Feedback session. Subjects will receive motivational enhancement counseling related to their drinking.

## 2) Subject recruitment and selection

Subjects for this study will be similar to those recruited during our previous studies. Individuals who meet *DSM-5* criteria for AUD, but who are not seeking treatment, will be recruited via the ARC Clinical Intake and Assessment Core, which will also collect blood for DNA extraction and prospective COMT genotyping. For inclusion in this study, individuals will be required to be between ages 21 and 40 (to match the current ARC sample in which we have demonstrated an APZ by COMT val158met interaction), to be physically healthy with no history of liver disease and normal liver function (to reduce risk of tolcapone hepatotoxicity), to have no current Axis I psychiatric disorder, to be taking no psychoactive medications or medications contraindicated with tolcapone, to have no current non-alcohol substance use except nicotine, and to have no MRI contraindications (e.g., neurological disease, history of head injury, implanted metal).

### Inclusion Criteria:

1. Age 21-40 (to focus on an age group still on a trajectory of increasing alcohol consumption).
2. Meets *Diagnostic and Statistical Manual of Mental Disorders, 5th edition (DSM-5)* criteria for current Alcohol Use Disorder.
3. Reports drinking, on average, at least 20 standard alcoholic drinks per week for at least the past 3 months.
4. Currently not engaged in, and does not want treatment for, alcohol-related problems.
5. Able to read and understand questionnaires and informed consent.
6. Lives within 50 miles of the study site.
7. Able to maintain abstinence from alcohol for two days (without the aid of detoxification medications), as determined by self-report and saliva alcohol measurements.

### Exclusion Criteria:

1. Current *DSM-5* diagnosis of any other substance use disorder except Nicotine Use Disorder.
2. Any psychoactive substance use (except marijuana and nicotine) within the last 30 days, as indicated by self-report and urine drug screen. For marijuana, no use within the last seven days by verbal report and negative (or decreasing) urine THC levels.
3. Current *DSM-5* Axis I diagnosis, including major depression, panic disorder, obsessive-compulsive disorder, post-traumatic stress disorder, bipolar affective disorder, schizophrenia, dissociative disorders, eating disorders, or any other psychotic or organic mental disorder.
4. Current suicidal ideation or homicidal ideation.
5. Need for maintenance or acute treatment with any psychoactive medication, including antiepileptic medications.
6. Currently taking medication known to affect alcohol intake (e.g., disulfiram, naltrexone, acamprosate, topiramate).
7. History of severe alcohol withdrawal (e.g., seizure, delirium tremens), as evidenced by self-report and assessment with Clinical Institute Withdrawal Assessment for Alcohol-Revised (CIWA-Ar).

8. Clinically significant medical problems such as cardiovascular, renal, gastrointestinal, or endocrine problems that would impair participation or limit medication ingestion.
9. Past alcohol-related medical illness, such as gastrointestinal bleeding, pancreatitis, or peptic ulcer.
10. Current or past hepatocellular disease, as indicated by verbal report or elevations of SGPT (ALT) or SGOT (AST) greater than the upper limit of the normal range at screening.
11. Females of childbearing potential who are pregnant (by urine HCG), nursing, or who are not using a reliable form of birth control.
12. Current charges pending for a violent crime (not including DUI-related offenses).
13. Lack of a stable living situation.
14. Presence of ferrous metal in the body, as evidenced by metal screening and self-report.
15. Severe claustrophobia or morbid obesity that preclude placement in the MRI scanner.
16. History of head injury with > 2 minutes of unconsciousness.

### 3) Medication safety, adherence, and dosing

**a) Safety.** Associations between variation at the COMT val158met SNP and a variety of psychiatric phenotypes (18) have suggested that tolcapone and other COMT inhibitors might be efficacious for individuals with psychiatric disorders, including depression (60) and schizophrenia (61; 62). However, despite this potential, several reports of severe liver toxicity have reduced enthusiasm for further study. There was no indication of toxicity in preclinical work with tolcapone, and clinical trial data suggested only a 1-3% greater incidence of abnormal elevation of liver enzymes (i.e., alanine transaminase [ALT] and aspartate transaminase [AST]) over placebo (63). Nevertheless, in the first years of clinical use, four of approximately 60,000 patients, dosed with tolcapone for two to four months, developed severe liver toxicity, with three deaths reported (63). Based on this, the FDA recommended routine liver function tests (LFTs) for patients receiving tolcapone (biweekly for the first year of treatment).

Most of the other side effects associated with tolcapone (sleep problems, hallucinations, dystonia) are related to its combined use with L-DOPA for the treatment of Parkinson's disease (64). Significant diarrhea, however, seems to be specific to tolcapone and has been reported even when used alone. Overall, other than idiosyncratic liver toxicity, tolcapone is well tolerated and a reasonably safe drug when used independently of L-DOPA, as demonstrated in the studies of smokers (49) and pathological gamblers (48) discussed above. Importantly, neither liver enzyme elevation nor other adverse events were noted in either of these studies.

Nonetheless, given past reports of liver toxicity, caution is in order and reduction of risk is required. Subjects in this study will take tolcapone for only seven days, a period shorter than the FDA's first recommended interval for LFTs (after two weeks of dosing). However, heavy-drinking subjects may be at increased risk for liver compromise. Therefore, only individuals who 1) report no history of past liver disease and 2) have normal liver enzymes prior to randomization will be enrolled in the study. In our current ARC study, 23% of subjects had elevated liver enzymes; thus, we do not anticipate that this exclusion criterion will unduly limit recruitment. Subjects will be contacted on day 4, after they have taken medication for three days, to inquire about their wellbeing, including any complaints of abdominal pain, gastrointestinal disturbance, extreme fatigue, or skin color change. If any liver-related complaints are present on day 4, subjects will be discontinued from further study. These symptoms will also be assessed in person on day 7, and LFTs will be repeated on day 7 or 8, after medication administration is complete; if liver-related complaints are present or liver enzymes are elevated at that time, we will continue to monitor until they return to normal, and/or consider a referral to a hepatologist. To date, we have used this procedure in ten individuals who completed a prior pilot study and over 70 who have been enrolled in the current protocol; it has worked well.

**b) Adherence.** Given that subjects will not be seeking treatment, adherence to medication ingestion could be of concern. To monitor adherence, study medication will be over-encapsulated with 25 mg of riboflavin (which, in our experience, yields urine levels 2-3x normal basal levels up to 24 hours after medication ingestion), and urinary riboflavin will be measured in the CNL. Urine will be collected twice at baseline (to obtain a more valid average daily output) and on day 7. A spectrofluorometric assay with known aqueous standards will be used to develop a standard fluorescence curve from which to read the fluorescence of urine samples. Riboflavin levels will be compared between medication and genotype groups; levels > 1500 ug/ml will be considered adherent. Although urinary riboflavin is not a perfect measurement of adherence,

**c) Dosing.** Subjects will be instructed to take medication capsules (each containing either placebo or 100 or 200 mg of tolcapone) in the morning, at noon, and in the evening on the schedule shown in **Table 3**. On day 7, subjects will take their final dose between 11 am and 2 pm, at least one hour before the final brain scan.

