**6).** The onset latency between the appearance of the target and the stop signal begins at 189 ms and increases by 67 ms (i.e., becomes more difficult) if the subject is able to withhold his or her response to that trial; conversely, onset latency decreases by the same amount if the subject fails to inhibit his or her response. This “psychophysiological staircase” procedure (69) ensures that all subjects perform the task equivalently, thereby removing behavioral variance and allowing isolation of the neural substrates of response inhibition. Responses must be made within 1 s of stimulus presentation, and the inter-trial interval varies randomly between 1 and 4 s, allowing subjects to develop a prepotent “go” response to the more frequent targets that are not followed by stop signals, but preventing rhythmicity in responding. To ensure a sufficient number of the less frequent stop trials, three 10-m gradient-echo EPI runs of the task will be acquired (parameters: TR/TE= 2000/25 ms; FA= 85°; FOV= 220 x 220 mm; voxel size = 3.44 x 3.44 mm; 32 contiguous 4-mm-thick slices).

**Figure 6.** Target stimulus (left) and stop signal (right) from the response inhibition task.

**b) Natural drinking period (days 1-6).** Subjects will be given no specific instructions regarding their drinking during the first six days of study medication ingestion. On day 7, before the scan, subjects will report their drinking over the previous six days using the Timeline Follow-back calendar method (70).

**c) Post-treatment scan session (day 7).** Subjects will again give a breath or saliva sample for alcohol testing and assessed for alcohol withdrawal symptoms, and the functional sequences acquired during the pre-treatment scan will be repeated. At this visit or the following day (day 8), blood for LFTs and the COMT activity assay will also be collected.

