**c) Randomization plan.** *COMT* genotype will be used to prospectively randomize subjects to tolcapone or placebo medication. The *COMT* val/val genotype is more frequent among African-Americans (AA) than among European-Americans (EA), the two primary racial groups in the Charleston, SC area. In our preliminary data, 16% of subjects were AA and 83% were EA, consistent with the usual racial distribution of our studies. Val/val genotype frequency was 0.70 among AA and 0.25 among EA, consistent with dbSNP allele frequency estimates (Asian-Americans, who have comprised ~5% of our past study populations, have val/val frequencies similar to AA). To account for racial differences in val-allele frequency, we will stratify subjects by race (AA/Asian vs. EA) and *COMT* genotype (val/val, val/met, or met/met), and will then urn randomize subjects to tolcapone or placebo. Since some recent data suggest that the effects of both tolcapone (82) and *COMT* variation (83; 84) differ by sex, sex will be used as the urn variable within each of these six strata. The **ARC Biostatistics Core** statistician will oversee this process.

**d) Aim 1: Evaluate tolcapone and *COMT* val158met effects on drinking in the natural environment during six days of treatment.**

**1. Analysis and expected results.** Analyses for all aims will be conducted with consultation from the **ARC Biostatistics Core** statistician. The main dependent variable for Aim 1 will be drinking under natural conditions during days 1-6 (drinks per day). The general linear model (GLM) will be used to analyze the main effects of tolcapone and *COMT* genotype, as well as their interaction, on this variable. Pre-treatment drinking will be included as a covariate in these models, as will any salient demographic variables (e.g., age, cigarette smoking, family history of alcoholism). We predict that tolcapone, relative to placebo, will reduce natural drinking, and will do so to a greater extent among *COMT* val-allele homozygotes.

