4. To further minimize the risks of liver damage, subjects who are randomized to tolcapone will take this medication for only seven days, which is shorter than the first FDA-recommended liver enzyme test date (two weeks of dosing). However, we recognize that those heavily consuming alcohol may be at increased risk for liver compromise. Therefore, we will contact subjects after they have taken medication for three days (i.e., on study day 4) to inquire about their wellbeing, including checking for any complaints of abdominal pain, gastrointestinal disturbance, extreme fatigue or skin color change. These symptoms will also be assessed in person on study day 7. Liver enzyme tests will be repeated on study day 7 or 8, after medication administration is complete. If any possible liver-related side effects are present on study day 4, subjects will be discontinued from further study. If liver enzymes are elevated above the upper limit of the normal range on study day 7 or 8, or possible liver-related side effects are present on this day, we will continue to monitor liver enzymes until they return to normal and/or consider a referral to a hepatologist.
5. To minimize other risks associated with study medication ingestion, all subjects will be given a card that states that they are participating in a research study and may be taking tolcapone, and the name of the PI or his designate will be provided for emergency contact. During the course of the study, medical coverage will be provided for emergency situations. To minimize medication side effects, the dose of tolcapone will be titrated up over several days.
6. To minimize risks associated with MRI, all subjects will be screened for metal in their bodies, as well as for claustrophobia. Metal found, particularly around the head and neck area, will be exclusionary for participation. Metal in other areas of the body will be evaluated by trained technical staff prior to magnetic exposure. An anatomical brain image will be collected and reviewed for any significant brain pathology before proceeding with the scan. During the scan, subjects may stop the procedure at any time if they feel overly anxious or claustrophobic.

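### Discontinuing a subject on day 4 for a liver-related complaint also forfeits the day-7 drinking outcome, and the plan has no rule for that loss

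*Combined protocol and SAP*

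**What the plan says.** Section B.3 a) has staff contact subjects on day 4 about their wellbeing, "including any complaints of abdominal pain, gastrointestinal disturbance, extreme fatigue, or skin color change". It continues: "If any liver-related complaints are present on day 4, subjects will be discontinued from further study". Section C.2 b), item 4, repeats the rule with a slightly different trigger: "If any possible liver-related side effects are present on study day 4, subjects will be discontinued from further study". Both passages end study participation, not only dosing.

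The main Aim 1 variable (B.5 d) is average daily drinking over days 1-6. B.4 b) fixes when it is obtained: "On day 7, before the scan, subjects will report their drinking over the previous six days". No other collection point for on-treatment drinking is described.

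On tolerability, B.3 a) says: "Significant diarrhea, however, seems to be specific to tolcapone and has been reported even when used alone". Of the studies in smokers and gamblers it also says that "neither liver enzyme elevation nor other adverse events were noted in either of these studies". On the day-4 procedure it says: "To date, we have used this procedure in ten individuals who completed a prior pilot study and over 70 who have been enrolled", and it expresses satisfaction with how this went. It does not say how many subjects were discontinued, overall or by arm.

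Section B.5 names no analysis population for Aim 1, no method for missing outcomes, no sensitivity analysis and no dropout allowance. The full 90 is used for power.

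**The concern.** Removing a subject on day 4 removes the outcome as well, because the six-day drinking calendar is taken three days later. The model can then use only those who reach day 7.

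Loss matters most when it depends on both arm and drinking. The arm link is possible: gastrointestinal disturbance is among the symptoms asked about on day 4, and the protocol attributes diarrhea to tolcapone itself. The drinking link is an inference: abdominal pain, stomach upset and fatigue are plausible in heavier drinkers. If both hold, heavier drinkers leave the tolcapone arm more often, and the completers show less drinking on tolcapone even if the drug does nothing. That would distort the tolcapone main effect, which is one of the two Aim 1 predictions. Any loss also costs power, since no allowance was made.

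**Working it through.** **Inputs from the documents.** N = 90, allocated 1:1 (C.1 a); 30 per genotype group, so 15 per arm-by-genotype cell; tolcapone effect 1.3 SD in val/val; stated interaction power 0.8 (B.5 b); pre-treatment drinking as a covariate (B.5 d).

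**Assumptions, because the documents give no figure.** Two-sided alpha 0.05; effects of 0, 0 and 1.3 SD in the three genotypes; removal rates of 10% vs 3%, 20% vs 5% and 30% vs 10% (tolcapone vs placebo); correlation r of 0.3 or 0.5 between complaint risk and drinking; baseline-to-outcome correlation 0.7.

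**1. The plan's own power.** Each genotype has weight w = 1/(1/15 + 1/15) = 7.5. For val/val against the mean of the other two genotypes, the contrast is 1.3 and its variance is (0.25 + 0.25 + 1)/7.5 = 0.20. Noncentrality = 1.69/0.20 = 8.45 on 1 and 84 df, giving power 0.82. This reproduces the stated 0.8. The 2-df interaction has the same noncentrality and gives 0.73.

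**2. Power after loss.** Loss is taken as equal across genotypes.

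| Removal, tolcapone vs placebo | Lost of 90 | w | Noncentrality, 1.69 × w/1.5 | Power, 1-df | Power, 2-df |
|---|---|---|---|---|---|
| none | 0 | 7.50 | 8.45 | 0.82 | 0.73 |
| 10% vs 3% | 4.5 + 1.35 = 5.85 (6.5%) | 7.00 | 7.89 | 0.79 | 0.69 |
| 20% vs 5% | 9 + 2.25 = 11.25 (12.5%) | 6.51 | 7.34 | 0.76 | 0.66 |
| 30% vs 10% | 13.5 + 4.5 = 18 (20%) | 5.91 | 6.65 | 0.72 | 0.61 |

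**3. Bias in the tolcapone main effect, no covariate.** Let a subject be removed when a normally distributed complaint risk, correlated r with on-study drinking, exceeds the cut-off z that removes a fraction q. Mean drinking among those kept then shifts by −r × φ(z)/(1 − q) SD, where φ is the standard normal density. The bias is the tolcapone shift minus the placebo shift.

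- 10% vs 3%, r = 0.3: −0.058 − (−0.021) = −0.04 SD
- 20% vs 5%, r = 0.5: −0.175 − (−0.054) = −0.12 SD
- 30% vs 10%, r = 0.5: −0.248 − (−0.097) = −0.15 SD

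Simulation with 45 per arm and no drug effect gives the same biases and type I error of about 5%, 8% and 10%.

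**4. Bias with the planned covariate.** The same simulation, adjusting for pre-treatment drinking:

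- If complaint risk acts on on-study drinking itself, the bias is −0.02, −0.06 and −0.08 SD, with type I error about 5%, 7% and 8%.
- If complaint risk acts only through habitual (baseline) drinking, the bias is about 0 and type I error about 5% in all three scenarios.

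**5. Interaction test.** With the covariate and loss equal across genotypes, the 2-df interaction test kept a type I error of about 5% in every scenario. Loss that differed by genotype as well as arm would not cancel in this way.

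**The case against.** The strongest reply is that the documents do not show the loss to be large or unequal. Four parts of it stand.

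- **The trigger.** A reader might infer that any gastrointestinal, pain or fatigue complaint on day 4 removes a subject. The text does not say so. The symptom list describes what staff ask about; the rule refers to liver-related complaints, and B.3 a) discusses diarrhea among the side effects other than liver toxicity. The broad reading is possible because the term is undefined, but a narrower reading would remove fewer subjects.
- **The rate.** A reader might infer that loss is likely to be higher on tolcapone. No rate supports that. The statement of no adverse events in two addiction studies, one of which gave 200 mg three times daily for eight days, points the other way, as does the favourable account of the day-4 procedure. Neither settles the matter, because no discontinuation count is given. The one pilot discontinuation (section 4, Tolcapone preliminary data) is described with a liver enzyme elevation, not a day-4 complaint.
- **The model.** The planned covariate removes roughly half of the bias or all of it, depending on mechanism. A baseline correlation weaker than 0.7 would remove less.
- **The powered test.** The sample size rests on the interaction, which is largely protected when loss is equal across genotypes.

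A reader might also infer that B.3 a) and C.2 b) conflict on liver tests, or that discontinued subjects lose theirs. The two sections agree with each other. They are silent on whether the day-7/8 tests apply to subjects removed on day 4, and silence is not a contradiction.

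The reply leaves the gap itself untouched: participation ends, the outcome is taken later, and nothing recovers it or says how to analyse without it.

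**Conclusion.** The concern holds as a gap in data collection and analysis, of unknown size. Subjects discontinued on day 4 contribute no Aim 1 outcome, and the analysis becomes one of completers without the plan saying so. The loss may depend on arm if liver-related is read to include gastrointestinal complaints; the documents do not establish that it does.

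Under the assumed removal rates, the main-effect bias is about 0.04-0.15 SD unadjusted and about 0-0.08 SD in the planned model, where type I error is about 5-8%. With a positive link between complaints and drinking, the bias imitates a benefit of tolcapone. Equal removal in both arms, with the same link to drinking, would give no bias. At 20% total loss, 1-df interaction power falls from 0.82 to 0.72, and 2-df power from 0.73 to 0.61. The documents do not support a claim that the arms will cease to be comparable, or that the interaction result is compromised. The gap should be closed because doing so is cheap.

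**What to change.** Leave the day-4 safety rule as it is, and add the following to the protocol and analysis plan before the blind is broken in year 5.

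- State that stopping study medication does not end outcome collection. Obtain the days 1-6 Timeline Follow-back from every randomized subject, by telephone if the subject does not attend on day 7.
- Analyse Aim 1 with all subjects as randomized, and give the completer analysis as a sensitivity analysis.
- Report day-4 discontinuations by arm and genotype. With over 70 subjects already enrolled, the overall count can be checked now, and the split can follow at unblinding.
- Clarify whether the day-7/8 liver tests apply to subjects discontinued on day 4.

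The cost is a few telephone interviews and a short amendment. Days after stopping are off drug, so the estimate is an effect of assignment and may be slightly smaller. The call recovers drinking data only: the second scan for Aim 2 is still lost. Nor does it help subjects already discontinued without a calendar; their number should be reported as missing outcomes.

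### As printed, the urinary riboflavin cut-off for adherence (> 1500 ug/ml) cannot plausibly be reached with 25 mg of riboflavin per capsule; its value and unit need checking against source

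*Combined protocol and SAP*

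**What the plan says.** Section B.3.b (Adherence) notes that adherence may be a problem because subjects are not seeking treatment. It therefore specifies that "study medication will be over-encapsulated with 25 mg of riboflavin", and reports from the team's experience that this "yields urine levels 2-3x normal basal levels up to 24 hours after medication ingestion". On sampling, "Urine will be collected twice at baseline" and once more on day 7. No collection volume, timed collection or creatinine correction is given. Two uses of the result follow: "Riboflavin levels will be compared between medication and genotype groups", and "levels > 1500 ug/ml will be considered adherent". The paragraph then breaks off in the provided text, just after "Although urinary riboflavin is not a perfect measurement of adherence".

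Section B.3.c (Dosing) describes the capsules as "each containing either placebo or 100 or 200 mg of tolcapone", taken "in the morning, at noon, and in the evening". Table 3 gives two doses on day 1, three on each of days 2 to 6, and two on day 7.

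Two other places bear on the point. Section A.4 (Tolcapone preliminary data) reports that urinary riboflavin showed every open-label pilot subject to be adherent, but gives no cut-off, unit or riboflavin dose. Section B.5.d.2 (COMT activity assay) names adherence as one purpose of the red-cell COMT measurement.

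**The concern.** A cut-off of 1500 ug/ml is 1.5 mg of riboflavin in every millilitre of urine. Set beside a dose of 25 mg per capsule, that looks far too high for any ordinary volume of urine. A cut-off that no one can pass does not classify: fully adherent subjects and subjects who took nothing would fall on the same side.

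This is the only numeric adherence rule in the visible text. An adherence rate is also what a reader would want beside a null drinking result, to judge whether the drug failed or was not taken. Red-cell COMT activity can help in the tolcapone arm, but placebo should not inhibit COMT, so it cannot show whether placebo capsules were taken. In that arm riboflavin is the only biological marker visible. A threshold changed after unblinding would be open to challenge.

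**Working it through.** The document gives no derivation of the cut-off, so there is no planned calculation to reproduce. The check is a mass balance.

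**Inputs from the documents**
- Riboflavin: 25 mg, read as per capsule (B.3.b).
- Capsules: at most 3 a day, and 2 on day 7 (B.3.c, Table 3). Whole course: 2+3+3+3+3+3+2 = 19.
- Cut-off: more than 1500 ug/ml, that is, 1.5 mg/ml (B.3.b).

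**Assumptions, not in the documents**
- Urinary recovery of 100%, the case most favourable to reaching the cut-off.
- Urine output of 0.5 to 3 L a day.

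**Formula.** Concentration (ug/ml) = dose (mg) × 1000 × recovery / volume (ml).

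**Level from the capsules, as a daily average**

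| Riboflavin | 0.5 L | 3 L | Shortfall against 1500 |
|---|---|---|---|
| Full day, 3 × 25 = 75 mg | 75,000/500 = 150 | 75,000/3000 = 25 | 1500/150 = 10 to 1500/25 = 60 times |
| Day 7, 2 × 25 = 50 mg | 50,000/500 = 100 | 50,000/3000 = 16.7 | 1500/100 = 15 to 1500/16.7 = 90 times |

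**Volume needed to reach 1500 ug/ml**
- Full day: 75 mg / 1.5 mg/ml = 50 ml.
- Day 7: 50 mg / 1.5 mg/ml = 33 ml.

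**Does another reading rescue it?**
- *Spot sample.* If a single void held the entire 75 mg, a 100 ml void would give 750 ug/ml. A 50 ml void would give exactly 1500, and the rule requires more than that.
- *Carry-over.* The whole course is 19 × 25 = 475 mg. If all of it appeared in one day's 0.5 L, the level would be 475,000/500 = 950 ug/ml.
- *25 mg as a daily total.* The gap becomes three times wider.
- *Basal riboflavin.* The documents do not quantify it, so it is left out above. A basal output equal to the capsule dose would double the levels: the full day would give 50-300 ug/ml, still 5-30 times short.

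**Alternative units, as illustration only**
- 1500 ng/ml is 1.5 ug/ml. It needs 0.75 mg in 0.5 L or 4.5 mg in 3 L, that is, 1-6% recovery of 75 mg.
- 1500 ug/day is 1.5 mg, or 2% of 75 mg.

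Both are attainable, so the arithmetic cannot choose between them.

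**The case against.** The strongest objection is that the point may turn on one character. The text was read from a PDF by a program, and a misread unit would be a conversion artefact, not an error in the plan. This stands: it cannot be excluded from the documents in hand, and it is why the source must be checked first. It does not remove the need for the check.

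The second objection is that little depends on the label. This also stands. The sample size, the primary general linear model and the mediation analysis do not use it, and group comparisons of measured riboflavin need no cut-off. Because the paragraph is cut, further adherence measures may follow.

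Third, the pilot report in A.4 counts against taking the printed number at face value. If the pilot used 25 mg, this cut-off could not plausibly have shown every subject adherent. That suggests a different value or unit in practice, though A.4 states none. So the literal result describes the rule as printed. A reader might infer a forecast that about 0% of this trial's subjects will be recorded as adherent; the documents do not support one.

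Fourth, urine volume and recovery are outside assumptions. They are, but recovery is set at its most favourable value and the smallest shortfall over the volume range is tenfold.

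A reader might also infer that the cut-off contradicts the stated two- to threefold rise over basal. No basal level is given, so the documents do not establish that contradiction.

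**Conclusion.** The point holds as a fault in the printed cut-off, with limited consequences. From the capsules alone, the attainable daily level is 25-150 ug/ml on a full dosing day and 17-100 ug/ml on day 7, against a threshold of 1500. The shortfalls are 10-60 and 15-90 times. These figures assume 100% recovery, 0.5-3 L of urine a day and 25 mg per capsule, with basal riboflavin excluded. Including a basal output as large as the capsule dose leaves the full-day level at least 5 times short.

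A reader might go further and conclude that subjects would be dropped, or that the Aim 1 result is compromised. The visible text does not support this: no exclusion, per-protocol set or efficacy model is tied to the label. Nor do the documents show that ng/ml was intended. The correction is worth making because the rule would not classify adherence as written and is cheap to repair. Confidence is medium, because the unit may have been misread in conversion.

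**What to change.** Before the blind is broken, compare the value and unit in B.3.b with the source document, then with the laboratory's standard curve and the rule it actually applies. If the source reads as printed here, correct the cut-off and record the basis for the corrected figure. If the source already shows another unit, confirm that it agrees with the laboratory's rule; if it does, no change to the plan is needed.

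The cost is one look-up and, at most, one corrected figure or unit. It needs no new samples, visits or analyses. Reporting the day-7 level relative to each subject's own baseline samples would be an optional description; it is a preference and not part of this correction.
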